### **Secondary Outcomes:**

- 1) To compare provider satisfaction with the reduction procedure between the two groups. Specifically, we will ask providers to determine:
  - I. Providers from experimental group:
    - a. Ease of fracture reduction - scale 1-5, (1=easy 5=very difficult)

---

Ang et al, Ultrasound-guided reduction of distal radius fractures, Am J of Emerg Med, 2010; 28, 1002-1008

Chinnock et al, Ultrasound-guided reduction of distal radius fractures, J of Emerg Med, 2011, 40 (3) 308-312

 Brahm J et al, A Randomized controlled trial of emergency department ultrasound-guided reduction of distal radius fractures, Annals of Emerg Med-Abstracts, 2011 Oct; 58(4), 230

IRB #:

Version 1.2

- b. Ease of using ultrasonography on a 5 point scale (1=easy, 5=very difficult).
- c. Was ultrasound helpful in completing the fracture reduction? a) yes b) no c) uncertain

II. Providers from control group:

- a. Ease of fracture reduction - scale 1-5, (1=easy 5=Most difficult)
- b. Do you think real-time imaging would have been helpful for this reduction?

|

- 2) To compare the adequacy of reduction between groups by measuring and comparing the degree of angulation and displacement on the post reduction x-rays. An orthopedic surgeon who is blinded to the patient's group assignment will read the x-rays. The acceptable degree of angulation will be the same in both groups. The acceptable degree of angulation based on age is less than 20 degrees' angulation for patients younger than 10 years of age and less than 10 degrees' angulation for patients older than 10 years of age.
- 3) To compare the time for the fracture reduction procedure between the experimental and control group.
- 4) To compare the number of patients requiring operative repair after reduction between the experimental and control group.
- 5) To compare the post-reduction ultrasound and x-ray interpretation, including measurement of degree of angulation and displacement on the ultrasound and x-ray for each patient.

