Consulting orthopedic residents will be trained to perform musculoskeletal sonography for this study (see below for standardized training of study physicians in ultrasound) and will be considered study-trained physicians. All patients will undergo procedural sedation and/or pain management for closed reduction as per standard of care in the PED. The medication used for sedation and/or pain will be determined by the treating PEM physician. Study patients that are randomized to the ultrasound guided group will undergo a point-of-care ultrasound, performed by a study trained physician using a Sonosite Edge ultrasound machine with an L38 linear 10-5 MHz transducer probe.

Prior to the reduction procedure in patients randomized to the experimental group, ultrasound images of the fracture site will be obtained and the maximum degree of displacement will be measured. The ultrasound technique involves placing ultrasound gel over the fracture site and then placing the ultrasound probe in contact with the gel but not with the underlying skin. Both longitudinal and transverse views of the injured area will be obtained. Fractures are identified as an irregularity or interruption of the cortex of the bone. The degree of displacement is measured by drawing two intersecting lines along the edge of the cortex at the fracture site, generating an angle. Displacement measurements are then made by calculating the distance from the normal cortex to the fractured edge of the cortex.

The trained physician will then perform real-time ultrasound imaging as needed during the closed reduction procedure. Real-time ultrasound imaging includes both longitudinal and transverse views of the fracture site, repeated as often as necessary until the best alignment can be obtained. Once the orthopedic resident determines that he/she has obtained optimal alignment and prior to casting, a post-reduction ultrasound image will be obtained and the angle of displacement will again be measured. All ultrasounds performed prior to and after the reduction will be recorded, and the images obtained will include video clips of the ultrasound as well as a saved still picture of the best image of the suspected fracture site. The study-trained physician who performed the ultrasound will then record his/her findings on the data collection form immediately after the procedure and prior to reviewing plain radiographs.

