While it has been our experience that the majority of reduction procedures performed in the PED are done without the use of any real time imaging, some orthopedic surgery residents employ the use of the c-arm (fluoroscopy) and/or a portable x-ray machine during the reduction procedure. At his/her discretion, the orthopedic resident may use either of these modalities in both the ultrasound and control group as per standard of care in the PED. The use of these modalities will be recorded.

After the reduction procedure in the ultrasound group and prior to reviewing the post reduction x-ray, the orthopedic resident will complete a brief questionnaire with the following questions.

For the experimental group:

- a. Rate the ease of fracture reduction from 1-5, (1=easy 5=Very difficult)
- b. Was ultrasound helpful in completing the fracture reduction? a) yes b) no c) uncertain
- c. Rate the ease of using ultrasonography on a 5 point scale (1- easy, 5=very difficult).

The control group will undergo fracture reduction without ultrasound guidance as per the current standard of care in the PED. After the reduction procedure in the control group, the orthopedic resident will complete a brief questionnaire with the following questions:

For the control group:

IRB #:

Version 1.2

- a. Rate the ease of fracture reduction from 1-5, (1=easy 5=very difficult)
- b. Do you think real-time imaging would have been helpful for this reduction?

After the reduction and casting is completed, patients in both groups will undergo a post-reduction x-ray. Based on the degree of displacement on the x-ray, the orthopedic surgeon will determine whether the patient needs a repeat reduction, as per routine standard of care. If a repeat reduction is required, the treating physician can choose to use ultrasound at his/her discretion. The angle of displacement will be measured on the post-reduction x-ray by an orthopedic surgeon. Additionally, the angle of displacement measured on the post-reduction ultrasound will be measured and compared to the angle of displacement on the post-reduction x-ray. An expert sonographer will review cases where the ultrasound and x-ray results do not correlate.

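### Some post-reduction ultrasound angles may be measured after an x-ray view of the same reduction has been seen, and secondary outcome 5 does not report those patients separately

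*Combined protocol and SAP*

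**What the plan says.** Secondary outcome 5 is "To compare the post-reduction ultrasound and x-ray interpretation, including measurement of degree of angulation and displacement on the ultrasound and x-ray for each patient". Section IIIa repeats the comparison for the angle: "the angle of displacement measured on the post-reduction ultrasound will be measured and compared to the angle of displacement on the post-reduction x-ray". Only the experimental arm has a protocol ultrasound, so in practice this is a within-arm comparison.

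The ultrasound reading is taken once the resident judges alignment to be optimal: "prior to casting, a post-reduction ultrasound image will be obtained and the angle of displacement will again be measured". The physician who performed the ultrasound "will then record his/her findings on the data collection form immediately after the procedure and prior to reviewing plain radiographs".

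Section IIIa also notes that "some orthopedic surgery residents employ the use of the c-arm (fluoroscopy) and/or a portable x-ray machine during the reduction procedure", and that, at his or her discretion, "the orthopedic resident may use either of these modalities in both the ultrasound and control group". It adds: "The use of these modalities will be recorded". No analysis use of that record is described, either there or in the statistical paragraph under Number of Subjects.

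Section Ic limits blinding to the orthopedic surgeon who reads the x-rays. It does not cover the person measuring the ultrasound angle.

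**The concern.** A comparison of two measurement methods is informative about one method alone only if its reader does not know what the other shows. The recording rule in Section IIIa serves that purpose for films reviewed after the procedure. It does not clearly cover an x-ray view obtained during the procedure, which comes before the post-reduction ultrasound measurement.

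An operator who has just seen alignment on a c-arm or portable film may, knowingly or not, place the ultrasound measurement lines to match it. If such patients are pooled with the rest, the reported agreement describes a mixture of ultrasound alone and ultrasound after x-ray. A reader would take it as evidence on the first. This matters because the protocol's own background cites a pediatric study in which ultrasound had 50% sensitivity for an inadequately reduced fracture. How far post-reduction ultrasound can be trusted is therefore still open.

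**Working it through.** **1. Order of events in the ultrasound arm (Section IIIa).**

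| Step | Event | X-ray information available to the ultrasound measurer |
|---|---|---|
| 1 | Reduction under ultrasound; c-arm or portable x-ray allowed | Possibly, if used and seen |
| 2 | Alignment judged optimal; post-reduction ultrasound angle measured before casting | Whatever was seen in step 1 |
| 3 | Ultrasound findings recorded before plain radiographs are reviewed | As in step 2 |
| 4 | Casting, then post-reduction x-ray (the reference) | Not available at steps 2 and 3 |

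The rule at step 3 shields the reading from step 4. Nothing shields it from step 1. A portable x-ray is itself a plain radiograph, so its use sits badly with the wording of the rule; fluoroscopy sits badly with its purpose.

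**2. The plan's own figure.** The planned size sets the number of paired readings. Inputs under Number of Subjects are 25% versus 6%, 80% power and alpha 0.05 (two-sided assumed). With a mean proportion of 0.155:

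n = [1.96·√(2·0.155·0.845) + 0.8416·√(0.25·0.75 + 0.06·0.94)]² / 0.19² = (1.003 + 0.416)² / 0.0361 ≈ 55.8, so 56 per group.

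This reproduces the stated 56 (power 80.2%). It is not in dispute; here it only sets the maximum at about 56 pairs.

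**3. How many pairs might be affected.** The protocol gives no rate. By assumption, use in 10%, 25%, 40% or just under 50% of 56 patients gives about 6, 14, 22 or up to 27 pairs. The last takes the statement that most reductions are done without real-time imaging as a ceiling. That statement describes usual practice, not an arm that already has ultrasound.

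**4. What pooling could do (illustration only).** Assume an SD of the ultrasound minus x-ray difference of 6 degrees with no prior image and 3 degrees after one, with no mean shift. Neither SD is in the protocol, and the protocol does not name limits of agreement as its method. With f the share affected, pooled SD = √[(1−f)·36 + f·9].

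- f = 0: SD 6; limits ±1.96·6 = ±11.8 degrees.
- f = 0.1: √33.3 = 5.77; limits ±11.3 degrees (4% narrower).
- f = 0.4: √25.2 = 5.02; limits ±9.8 degrees (16% narrower).

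The whole effect comes from the assumed halving of the SD. If the SD is also 6 degrees in the imaged patients, nothing changes. If imaging is used for harder fractures and their SD is above 6, the pooled limits widen instead.

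**5. Precision cost of the subset without prior imaging.** At equal SD, the interval width grows by √(56/n).

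- 6 excluded: √(56/50) = 1.06.
- 14 excluded: √(56/42) = 1.15.
- 22 excluded: √(56/34) = 1.28.
- 27 excluded: √(56/29) = 1.39.

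With 22 excluded and the SDs assumed in step 4, the ratio to the pooled interval is 1.28·6/5.02 = 1.53.

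**The case against.** The strongest reply is that nobody can have seen the reference. The post-reduction x-ray is taken after casting, the ultrasound angle is measured before it, and the x-ray reader is blinded. The questionnaire rule in Section IIIa speaks of the post-reduction x-ray, so plain radiographs in the recording rule may mean only those films. This stands. A reader might infer that the ultrasound reading is unblinded to the reference film itself; the documents do not support that. What remains is possible knowledge of a different x-ray view of the same reduction.

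Second, exposure is not certain. A view during the reduction may precede further manipulation. PEM attendings and fellows are trained as well as residents, so the person scanning need not be the one who used the c-arm. Section Ia says that the institution is among the emergency departments not equipped for fluoroscopy. All this lowers the likely frequency and rules out treating every imaged case as contaminated. It does not remove the point: Section IIIa says that some residents use these modalities, and the Section Ia remark does not mention portable x-ray.

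Third, a reader might infer that agreement is necessarily inflated. Inflation is plausible, but discretionary use in harder fractures could worsen agreement in the same patients. The direction is likely, not established.

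Fourth, the plan has partial safeguards: use is recorded, still images and clips are stored, the angle is a defined geometric construction, and the statistical methods are to be developed further. These make a remedy easy, but none is one yet. The record as described covers use, not whether the measurer saw an image before measuring. No blinded re-reading is planned, and the expert sonographer reviews only cases where ultrasound and x-ray do not correlate, so agreement that is too good would not be picked up.

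**Conclusion.** The concern holds in a limited form. Section IIIa protects the ultrasound reading from the post-casting film but not from x-ray views obtained during the reduction, and no analysis separates the patients in whom such views were available. Agreement in secondary outcome 5 may therefore be overstated as a description of ultrasound alone.

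The size is unknown. The illustration of 4% to 16% narrower limits rests entirely on assumed usage of 10% to 40% and assumed SDs of 6 and 3 degrees; it is not an estimate for this trial. Fluoroscopy may be uncommon at the site, and case selection could offset the bias.

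The consequence is confined to one secondary, within-arm comparison. A reader might infer that the randomised comparison or the 56 per group is also compromised by this; nothing in this point supports that. The remedy is still worth adopting because it is nearly free, and whether an image was seen before the measurement is hard to reconstruct later.

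**What to change.** 1. Reconcile the two statements in Section IIIa by saying whether the recording rule is meant to cover c-arm and portable x-ray views obtained during the reduction. This is a clarification of wording; permitted imaging does not change.
2. Keep the planned record of c-arm and portable x-ray use, and add one tick-box to the data collection form: did the person measuring the ultrasound angle see any radiographic image of this reduction before recording the post-reduction angle?
3. Pre-specify that agreement for secondary outcome 5 is reported for all ultrasound-arm patients, and separately for those with and without such prior imaging. Any claim about ultrasound alone rests on the patients without it.
4. State the limitation alongside: prior imaging is discretionary, so the subset without it may contain easier fractures.

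The cost is one form item and a sentence or two in the analysis plan. The subset estimate is less precise: at equal SD, about 6% wider if 6 of 56 are excluded and about 28% wider if 22 are. Showing the all-patient result beside it keeps both the loss of precision and any selection visible.

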The use of ultrasound for real-time guidance of fracture reduction compared to blind reduction has been assessed in the adult literature. In a before-and-after study, Ang et al, compared ultrasound guided reduction to a retrospective control group who underwent blinded fracture reduction and showed a decreased rate in the number of repeat reductions. In a similar before-and-after study, Chinnock et al, showed no significant difference in successful reduction rates with ultrasound compared to blinded reduction. Brahm J et al, in an unpublished abstract, conducted a randomized, single blinded study of adult patients comparing ultrasound guided reduction to standard closed reduction of distal radius fractures and found no difference in the adequacy of reduction, time to reduction or number of repeat reductions between the groups.

It is apparent from these studies that there is a role for ultrasound in guiding fracture reduction. Using ultrasound for dynamic visualization instead of fluoroscopy has several advantages. Ultrasound provides no ionizing radiation, while fluoroscopy exposes the patient, caretaker, and provider to ionizing radiation, requiring shielding for all involved to minimize exposure. Fluoroscopy requires the use of a large, cumbersome machine and many emergency departments, including our institution, are not equipped with fluoroscopic equipment. We intend to build on the studies of Chen et al, Patel et al, and others, with a randomized controlled trial to compare the use of real-time ultrasound guidance of closed forearm fracture reduction to blinded closed forearm fracture reduction in the pediatric emergency department.

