### **III. METHODS AND PROCEDURES**

#### **IIIa. Methods and Procedures**

This will be a prospective randomized, controlled, single blinded study that will take place at the Children's Hospital at Montefiore (CHAM) in the Pediatric Emergency Department (PED). Patients who present to the PED, are confirmed to have a forearm fracture requiring closed reduction in the PED and meet the inclusion/exclusion criteria will be eligible for the study. The decision to perform a closed reduction procedure in the PED will be made by the consulting orthopedic surgeon who will perform the procedure. All eligible patients' pain will be reassessed and managed as necessary as per standard of care. The eligible patient or parent/guardian will be approached by the treating physician or consulting orthopedic resident for written consent. Written assent will be obtained from minors older than 7 years of age (see below for consent timeline/process). After enrollment into the study, patients will be randomized to either the experimental group (ultrasound guided fracture reduction) or control group (standard of care forearm fracture reduction without real-time imaging). Allocation of patients to intervention and control arms will be accomplished by a computer-generated permuted block randomization scheme. An individual in the Department of Orthopaedic Surgery, who is not part of the study team will perform block randomization and will provide the study team with sealed envelopes for treatment prior to the enrollment of any patients in the study. These envelopes will be part of the study package, which include study questionnaires. We will choose blocks of 20 patients in order to reduce or eliminate experimental error contributed by inexperience using the US-guidance at the beginning of the study.

IRB #:

Version 1.2

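### The control arm is defined as reduction without real-time imaging, yet c-arm or portable x-ray is allowed in both arms, so the trial cannot support a conclusion about ultrasound versus unguided reduction

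*Combined protocol and SAP*

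**What the plan says.** The comparator is described in three ways.

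- **No imaging guidance.** The closing paragraph of section Ia says the trial will "compare the use of real-time ultrasound guidance of closed forearm fracture reduction to blinded closed forearm fracture reduction". The randomization text in section IIIa names a "control group (standard of care forearm fracture reduction without real-time imaging".
- **Other imaging allowed.** Later in section IIIa, the protocol reports that some residents use a c-arm or a portable x-ray machine during the reduction. It then leaves the choice to the individual: "the orthopedic resident may use either of these modalities in both the ultrasound and control group as per standard of care in the PED". Further on, that section describes the control procedure as follows: "The control group will undergo fracture reduction without ultrasound guidance as per the current standard of care in the PED". That wording rules out ultrasound but no other imaging.
- **Standard of care, with no statement on imaging.** The primary outcome in section Ib, the sample size in section IIId (Number of Subjects) and the procedure summary in section VIa all use this description.

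On how often other imaging is used, section IIIa says only that "the majority of reduction procedures performed in the PED are done without the use of any real time imaging". It adds: "The use of these modalities will be recorded". No analysis of that record is specified. The regression in section IIId is generic and does not name imaging.

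On equipment, section Ia says that many emergency departments, "including our institution, are not equipped with fluoroscopic equipment".

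**The concern.** A control patient reduced under the c-arm complies with the permission in section IIIa but does not fit the control definition given earlier in the same section. Section Ia treats fluoroscopy as the alternative form of dynamic visualization, so such a patient receives help of the kind the trial sets out to test. Residents know the allocation, so use of the c-arm may also differ between arms even though the permission is the same.

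What is at stake is mainly the meaning of the result. A contrast with usual care that includes some image guidance is a valid question, but a different one from a contrast with unguided reduction. Section Ia makes the difference important: it faults an earlier ultrasound study for comparing with neither blinded reduction nor another real-time modality. This protocol would mix those two comparators in one control arm.

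A second possible consequence is a smaller difference between arms than the 19 percentage points planned for. Whether that happens depends on facts the documents do not give.

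**Working it through.** **Inputs.** Section IIId (Number of Subjects) gives a control rate of 25% (5 of 20 charts), an ultrasound rate of 6%, 56 patients per group, 80% power, alpha 0.05 and the chi-square test. Sidedness is not stated; two-sided is assumed.

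**The plan's own figure.** With pooled variance, no continuity correction and mean rate (0.25 + 0.06)/2 = 0.155:

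n = [1.96·√(2·0.155·0.845) + 0.842·√(0.25·0.75 + 0.06·0.94)]² / 0.19² = 55.8, rounded up to 56 per group.

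The stated 56 reproduces, so the sample-size arithmetic is not at fault. Power at 56 per group is 80.2% by the normal approximation. It is 82.7% when every pair of binomial outcomes is enumerated with the uncorrected chi-square. The exact method is used below.

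**What imaged controls could do to power.** Let f be the share of controls who receive other imaging and r their failure rate. Then:

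control rate = 0.25·(1 − f) + r·f

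This treats 25% as the rate for truly unguided reduction and holds the ultrasound arm at 6%. The documents give neither f nor r, so both are varied. Half benefit means r = (25% + 6%)/2 = 15.5%.

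| Share of controls imaged (f) | Power if r = 6% (equal to ultrasound) | Power if r = 15.5% (half the benefit) | Power if r = 25% (no benefit) |
|---|---|---|---|
| 0 | 83% | 83% | 83% |
| 10% | 76% | 79% | 83% |
| 20% | 68% | 76% | 83% |
| 30% | 58% | 72% | 83% |
| 40% | 48% | 68% | 83% |

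For example, at f = 30% and r = 6% the control rate is 0.25·0.7 + 0.06·0.3 = 19.3%. The difference is then 13.3 points instead of 19.

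**The other reading of the 25%.** The 20 charts come from closed reductions in the same emergency department, where section IIIa says some residents use the c-arm or x-ray. If those charts include such cases, 25% is already a usual-care rate. With practice unchanged, discretionary imaging then costs no power against usual care. But 25% would then not be the rate for reduction without real-time imaging, which is how section IIIa defines the control.

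**The case against.** The strongest reply is that this is a usual-care trial with some stray wording. The primary outcome, the sample size and the procedure summary all name standard of care as the control. Section Ia is background. The permission is the same in both arms, most reductions are said to use no real-time imaging, and any use is recorded. Much of this stands. A usual-care comparison is legitimate, and most of the operative text fits it. But the exclusion of real-time imaging sits in the randomization text itself and the stated aim repeats it, so the two readings must be reconciled.

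Several stronger readings are tempting, and the documents do not support them.

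- **That a null result would be uninterpretable.** It would show no demonstrated gain over usual care, which is the question in sections Ib and IIId.
- **That every imaged control shrinks the planned difference.** This holds only if 25% is an unguided rate and the other imaging helps.
- **That other imaging adds little in the ultrasound arm, so any bias runs against ultrasound.** Section Ia cites a study in which ultrasound had 50% sensitivity for inadequate reduction judged against fluoroscopy. C-arm use in the ultrasound arm could therefore catch failures and favor that arm. The direction of bias is not established.
- **That the fluoroscopy statements flatly contradict each other.** The emergency department may own no unit while orthopedic residents bring one. This needs clarifying, and scarce equipment would make imaged controls few.
- **That an instrumental-variable analysis using the assigned arm could recover the effect against unguided reduction.** One binary instrument cannot separate no imaging, other imaging and ultrasound. Dividing by (1 − f) returns 19 points only if other imaging equals ultrasound. At f = 30% it gives 16.15/0.7 = 23 points at half benefit and 19/0.7 = 27 at no benefit.

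Portable x-ray may also be intermittent rather than real-time, so the conflict is clearest for the c-arm.

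**Conclusion.** The inconsistency is real and concerns what the trial estimates. As written, the contrast is ultrasound with optional other imaging versus usual care with optional other imaging. That cannot support a conclusion about ultrasound versus unguided reduction, which is what section Ia and the randomization text of section IIIa call for.

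The effect on power is conditional and may be nil. The range in the table, from no loss down to 48%, rests on assumed shares of 10% to 40%, an assumed benefit of the other imaging, an ultrasound arm fixed at 6%, and 25% being an unguided rate. None of these is established in the documents. The figures show why the comparator should be fixed and the 25% traced to it; they do not show that the trial is underpowered. The point should be dealt with before enrollment, but it does not invalidate the design.

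**What to change.** 1. Reconcile sections Ia and IIIa into one stated comparator, consistent with Ib, IIId and VIa. Which imaging rule applies is the sponsor's clinical decision.
2. If discretionary imaging stays, state both the comparison and the planned conclusion as ultrasound versus usual care including discretionary c-arm or x-ray. Remove the exclusion of real-time imaging from the randomization text and the word *blinded* from the stated aim.
3. Pre-specify a table, by arm, of c-arm and portable x-ray use during the first reduction, from the data already to be recorded.
4. Check the 20 reviewed charts for such imaging and say which comparator the 25% represents.
5. Clarify how the statement in section Ia about fluoroscopic equipment fits with the c-arm use in section IIIa.

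The cost is protocol wording, one table and a re-read of 20 charts, with no added patients or procedures. The small downside is a less sharp headline claim if the comparator becomes usual care.

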#### **IIId. Number of Subjects**

From a retrospective chart review sampling of displaced forearm fractures requiring reduction from June 1 to August 31, 2015 at CHAM, there were 20 displaced forearm fractures that underwent a closed reduction procedure in the Pediatric Emergency Department. 5 of the 20 displaced forearm fractures (25%) were inadequately reduced and required repeat reduction and/or operative management. Based on a recent study by Wellsh et al, only 6% of patients required repeat fracture reduction when US guidance was used.

In order to observe such a difference with 80% power, the sample size calculation would require a minimum of 56 patients in each group (standard of care vs US-guided reduction) with alpha set at P= 0.05.

Statistical significance will be assessed using mean, percentages, frequency distributions, and p-value. The significance will be set at 0.05. The test statistic used will be the Chi-square test. Confidence intervals will also be obtained. After the primary analysis of the group differences, logistic or normal regression will be used to determine factors related to these outcomes. The significance will be set at 0.05. The statistical approaches will be further developed with the assistance of the statistician in the orthopaedic surgery department following data collection and study approval.

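### The satisfaction form must be completed before the post-reduction film is seen in the ultrasound arm, but not in the control arm, so the only item asked in both arms may be rated under different conditions

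*Combined protocol and SAP*

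**What the plan says.** Section IIIa (Methods and Procedures) times the questionnaire separately for each arm.

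- Ultrasound arm: "After the reduction procedure in the ultrasound group and prior to reviewing the post reduction x-ray, the orthopedic resident will complete a brief questionnaire".
- Control arm: "After the reduction procedure in the control group, the orthopedic resident will complete a brief questionnaire with the following questions". The film is not mentioned.

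Patients in both arms have a post-reduction x-ray once casting is done. The only other before-the-film rule in section IIIa applies to the physician who performed the ultrasound, who must "record his/her findings on the data collection form immediately after the procedure and prior to reviewing plain radiographs". That rule concerns ultrasound findings, so it cannot apply to controls.

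The Secondary Outcomes list plans a between-arm comparison of provider satisfaction and gives no timing. It words the top of the shared scale differently by arm: "Ease of fracture reduction - scale 1-5, (1=easy 5=very difficult" for ultrasound and "Ease of fracture reduction - scale 1-5, (1=easy 5=Most difficult" for control. Section IIIa uses the first of these wordings for both arms.

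**The concern.** Section Ib hypothesises that ultrasound will improve provider satisfaction. Of the questionnaire items, only ease of reduction is asked in both arms. Helpfulness of ultrasound and ease of using it are asked only in the ultrasound arm, and whether real-time imaging would have helped is asked only of controls. The between-arm satisfaction comparison therefore rests on one 1-5 rating.

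Section Ic blinds only the surgeon who reads the x-rays, so the residents giving this rating know the assignment. A resident who has just seen a poor film may recall the reduction as harder, and one who has seen a good film may recall it as easier. If this can happen in one arm and is ruled out in the other, part of any difference between arms may reflect when the form was completed. No completion time is recorded, so post-film ratings could be neither identified nor corrected later.

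**Working it through.** **Text check.** Four places could set the timing of the control form.

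1. Section IIIa, ultrasound-arm sentence: after the reduction and before the film.
2. Section IIIa, control-arm sentence: after the reduction only.
3. Section IIIa, rule on recording findings before radiographs: covers ultrasound findings only.
4. Secondary Outcomes: lists the items with no timing.

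None of them gives controls the x-ray condition. The text permits a post-film control rating but does not require one.

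**The plan's own sample size.** Section IIId (Number of Subjects) gives 25% versus 6%, 80% power, alpha 0.05 and 56 per group. The pooled two-proportion formula, two-sided and without continuity correction, has mean proportion 0.155:

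n = [1.960 × √(2 × 0.155 × 0.845) + 0.842 × √(0.25 × 0.75 + 0.06 × 0.94)]² / 0.19² = (1.003 + 0.416)² / 0.0361 ≈ 55.8, rounded up to 56.

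Power at 56 per group is 80.2%. The figure reproduces, and I use 56 per arm below. The timing point does not change it.

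**Illustration of size.** The inputs are:

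- 56 per arm, from section IIId.
- 25% of control films showing failure. This is a stand-in from the chart review in section IIId: "5 of the 20 displaced forearm fractures (25%) were inadequately reduced and required repeat reduction and/or operative management".
- SD of 1 point on the 1-5 scale (assumed).
- s, the share of control forms completed after the film (assumed).
- f and g, the shifts in rated difficulty after a failed film and a good film (assumed).

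Bias (control minus ultrasound difficulty) = s × (0.25 × f + 0.75 × g).

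SE of the difference in means = √(2/56) = 0.189.

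False-positive rate at two-sided 0.05 = Φ(δ − 1.96) + Φ(−δ − 1.96), with δ = bias/SE.

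| s | f | g | Bias (points) | δ | False-positive rate |
|---|---|---|---|---|---|
| 1 | 1 | 0 | +0.25 | 1.32 | 0.263 |
| 0.5 | 1 | 0 | +0.125 | 0.66 | 0.101 |
| 1 | 0.5 | 0 | +0.125 | 0.66 | 0.101 |
| 0.2 | 1 | 0 | +0.05 | 0.26 | 0.058 |
| 1 | 1 | -1/3 | 0 | 0 | 0.050 |
| 1 | 1 | -0.5 | -0.125 | -0.66 | 0.101 |

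In the first row the mixture of shifted and unshifted ratings also widens the control variance, to 1 + 0.25 × 0.75 = 1.1875. The SE becomes √((1 + 1.1875)/56) = 0.198, and the rate falls from 0.263 to 0.244.

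A positive bias favours ultrasound and a negative one goes against it. Both arise from plausible inputs.

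**The case against.** The strongest reply is that this is a drafting omission. Section IIIa describes the control form before it describes the x-ray, so a natural reading is reduction, form, casting, film in both arms. The ultrasound-arm condition may also have been written to protect the ultrasound-specific items. This makes an intended difference unlikely, but it does not close the gap. The ultrasound-arm sentence also comes before the x-ray paragraph, and the authors still wrote the condition there.

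A second reply is that the illustration proves nothing about this trial. That is largely right. The SD, the shifts and the share of late forms are assumed. The 25% counts repeat reduction and/or operative management in 20 charts, not failure on the first film. Section IIId names the Chi-square test, not a comparison of means, for the group comparison. The 26% figure also needs every control form to follow the film and good films to have no effect. The table shows what could happen and should not be used to grade the problem.

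A third reply is that matching the film timing does not equalise conditions. This stands. In the ultrasound arm, before casting, "a post-reduction ultrasound image will be obtained and the angle of displacement will again be measured", so those residents rate after feedback on alignment. In addition, "the orthopedic resident may use either of these modalities in both the ultrasound and control group", meaning c-arm or portable x-ray. All raters know the assignment. The difference that remains could be as large as the one removed. That limits what the fix achieves, but it is no reason to keep an avoidable difference as well.

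The differing scale wording is minor. Section IIIa, which sets out the questionnaire, uses one wording, and nothing shows that the printed forms differ.

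**Conclusion.** The concern holds. The plan sets unequal collection rules for the one satisfaction item it can compare between arms, and that item is rated by unblinded residents. Whether control forms would in fact follow the film is unknown, and neither the size nor the direction of any bias can be derived from the documents. Under the stated assumptions the bias runs from +0.25 to -0.125 points and the false-positive rate from 5% to about 26%, with the top value an extreme case. The consequence is confined to the provider-satisfaction outcome. It should be corrected because it is easily avoided and cannot be repaired after collection, but it does not threaten the trial's main conclusions.

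**What to change.** In section IIIa, add to the control-arm sentence the condition already used for the ultrasound arm: the form is completed before the resident views the post-reduction x-ray. Record the completion time on the form in both arms so that compliance can be checked. Use one wording for the top of the 1-5 ease scale in both arms, in Secondary Outcomes and in section IIIa.

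The cost is one phrase, one anchor word and one time field. The ultrasound arm already works under this rule, and neither sample size nor patient care changes. The report should still say that the ratings are unblinded and that imaging seen before the form is completed differs between arms.
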